7. PLANNED ANALYSIS

If not otherwise stated, tables and listings will be done separately for IV treatment groups and SC treatment groups.

Safety analysis (refer to [Section 7.8](#)) will be performed by [REDACTED] and will be presented in Sections 15.1 to 15.4 of the CTR and in Appendix 16.2 and 16.1.13.1.

Inferential statistical analyses of PK endpoints (refer to [Section 7.4.1](#) and [Section 7.6](#)) will also be performed by [REDACTED] and will be presented in Section 15.5 of the CTR and in Appendix 16.1.13.3.

Descriptive data analysis of PK parameters and concentrations will be performed by the department [REDACTED] at [REDACTED] and will be presented in Section 15.6 of the CTR.

Descriptive data analysis of ADA will be performed by the department [REDACTED] at [REDACTED] and will be presented in Section 15.8 of the CTR.

The format of the listings and tables will follow the BI standards (see BI-KMED-BDS-HTG-0045 ([6](#)) with the exception of those generated for PK-calculations ([5](#))).

The individual values of all subjects will be listed, sorted by treatment group, subject number, and visit.

The listings will be included in Appendix 16.2 of the CTR.

For end-of-text tables, the set of summary statistics for non-PK parameters is:

N	number non-missing observations
Mean	arithmetic mean
SD	standard deviation
Min	minimum
Median	median
Max	maximum

For analyte concentrations, the following descriptive statistics will additionally be calculated:

CV	arithmetic coefficient of variation
gMean	geometric mean
gCV	geometric coefficient of variation

For PK parameters, the following descriptive statistics will additionally be calculated:

CV	arithmetic coefficient of variation
gMean	geometric mean
gCV	geometric coefficient of variation
P10	10th percentile

Q1	1st quartile
Q3	3rd quartile
P90	90th percentile

The data format for descriptive statistics of concentrations will be identical with the data format of the respective concentrations. The descriptive statistics of PK parameters will be calculated using the individual values with the number of decimal places as provided by the evaluation program. Then the individual values as well as the descriptive statistics will be reported with three significant digits in the CTR.

Tabulations of frequencies for categorical data will include all possible categories and will display the number of observations in a category, as well as the percentage (%) for each treatment group. Percentages will be rounded to one decimal place and will be based on all subjects in the respective subject set whether they have non-missing values or not. The category 'missing' will be displayed only if there are actually missing values.

Exclusion of PK parameters

The ADS ADPP (PK parameters) contains column variables APEXC and APEXCO indicating inclusion/exclusion (APEXC) of a PK parameter and an analysis flag comment (APEXCO). All analyses based on the PKS will include parameters if they are not flagged for exclusion, that is APEXC is equal to "Included".

Exclusion of PK concentrations

The ADS ADPC (PK concentrations per time-point or per time-interval) contains column variables ACEXC or ACEXCO indicating inclusion/exclusion (ACEXC) of a concentration and an analysis flag comment (ACEXCO). Exclusion of a concentration depends on the analysis flag comment ACEXCO. For example, if ACEXCO is set to 'ALL CALC', the value will be excluded for all types of analyses based on concentrations. If ACEXCO is set to 'DESC STATS', the value will be excluded from descriptive evaluations per planned time point/time interval. If ACEXCO contains the addition 'TIME VIOLATION' or 'TIME DEVIATION', the value can be used for further analyses based on actual times. If ACEXCO is set to 'HALF LIFE', the value will be excluded from half-life calculation (and, as a consequence, any calculation that relies on λ_z) only; the value is included for all other analyses.

Further details are given in BI-KMED-TMCP-MAN-0014 "Noncompartmental PK/PD analyses of Clinical Studies" ([5](#)).

Preliminary and interim analysis

If required for early interaction with regulatory agency, a preliminary snapshot will be conducted once all IV subjects have completed the study. This snapshot includes the complete clinical data of the iv group, but without PK/ADA data.

Furthermore an interim lock will be conducted at a later time. This interim lock includes the complete clinical data of the iv group, inclusive PK/ADA data. An interim report for the IV analysis will be written. All analyses defined in this TSAP restricted to IV subjects will be

done for this interim analysis. For details on interim analysis, e.g. definition of topline results, please refer to [Section 9.1](#).

7.1 DEMOGRAPHIC AND OTHER BASELINE CHARACTERISTICS

Only descriptive statistics are planned for this section of the report, based on the TS.

The data will be summarised by treatment group and in total.

7.2 CONCOMITANT DISEASES AND MEDICATION

Frequency tables are planned for this section of the report, based on the TS.

Concomitant diseases will be coded using the latest version of the coding system of the Medical Dictionary for Drug Regulatory Activities (MedDRA). Medications will be coded using the latest version of the World Health Organization Drug Dictionary (WHO-DD). The coding version number will be displayed as a footnote in the respective output.

The diagnoses and medications will be listed. Subjects without any concomitant diagnoses or concomitant therapies should be marked with a “No” in the respective column.

The relevance of the concomitant therapies to the evaluation of PK will be decided no later than at the RPM/DBLM.

7.3 TREATMENT COMPLIANCE

Section 4.3 of the CTP: *Compliance will be assured by administration of all trial medication in the study centre under supervision of the investigating physician or a designee. The measured sample concentrations will provide additional confirmation of compliance.*

It is not intended to list the compliance separately. Any deviations from complete intake will be addressed in the RPM/DBLM (see [Section 6.2](#)) and described in the CTR.

7.4 PRIMARY ENDPOINTS

7.4.1 Primary analysis of the primary endpoints

Section 7.1.3 of the CTP: *The primary endpoint as specified in [Section 5.1](#) will be derived according to BI standards (BI-KMED-TMCP-MAN-0014). The analysis will be based on the PKS and will be descriptive in nature.*

For IV doses the dose proportionality of $AUC_{0-\infty}$ and C_{max} will be analysed.

Assessment of dose proportionality

Dose proportionality will be explored via graphical checks and if applicable via the power model stated below. The analysis will be performed for the PK endpoints AUC/C_{max} specified in section 5.1.

The power model describes the functional relationship between the dose level and PK endpoint on the log scale via

$$y_{km} = \log(x_{km}) = \mu + b \cdot \log(D_k) + e_{km},$$

where

- y_{km} logarithm of response (PK parameter) measured on subject m^{th} receiving dose k ,
- μ the overall mean,
- β slope parameter of linear regression line,
- D_k level of dose k , $k=1, 2, 3$,
- e_{km} the random error associated with the m^{th} subject who was administered dose k ($e_{km} \sim N(0, \sigma^2)$ iid).

This equation can be fit as a linear regression model.

The slope parameter β together with its two-sided 90% confidence interval will be estimated. Perfect dose proportionality would correspond to a slope of 1. Additionally, the r -fold change $r^{\beta-1}$ together with its 90% CI will be derived.

Graphical displays:

A regression plot will be performed, where the logarithm of dose is depicted versus logarithm of PK endpoint, including the estimated regression line from the power model and reference line of perfect proportionality ($\beta=1$).

This analysis will be based on the PKS.

7.4.2 Sensitivity analysis, subgroup analysis, exploratory analysis of the primary endpoints

Not applicable.

[figure not shown]

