	71	1680:00	8:00	ambulatory visit	X	X					X
	92 ±2	2184:00	8:00	ambulatory visit	X	X	X ¹⁵				X
	120 ±3	2856:00	8:00	ambulatory visit	X	X					X
	148 ±3	3528:00	8:00	ambulatory visit	X	X					X
3	176 ±3	4200:00	8:00	EoTrial ¹³	X	X	X ¹⁵	X	X	X	X ⁵

Proprietary confidential information © 2021 Boehringer Ingelheim International GmbH or one or more of its affiliated companies

1. Screening with subject information, informed consent as the first measure, includes physical examination, check of vital signs including temperature, RR, systolic and diastolic BP and PR, 12-lead ECG, safety laboratory parameters (under fasting conditions), pregnancy test, drug screening, demographics (including determination of body height and weight, smoking and alcohol history), relevant medical history, concomitant therapy and review of inclusion/exclusion criteria.
2. The time is approximate; procedures are to be performed and completed within three hours prior to drug administration. Within three hours prior to the planned dosing, planned time -2:00 will be used.
3. Laboratory tests (safety laboratory parameters) include clinical chemistry, haematology, coagulation and urinalysis; in addition at screening: serology (HBV, HCV, HIV, QuantiFERON TB test, FSH and estradiol evaluation in questionable cases for determining postmenopausal status), and drug screening.
4. PK sampling times may be adapted based on information obtained during trial conduct.
5. Standardised assessment of local tolerability using the criteria swelling, induration, heat, redness, pain or other findings.
6. If several actions are indicated at the same time point, the intake of meals will be the last action.
7. Confirmation of fitness includes physical examination.
8. ADA samples will be taken at baseline, Day 15, Day 29, Day 43, Day 57, Day 71, Day 92, Day 120, Day 148 and Day 176 (EoTrial).
9. First measure after completion of infusion collection of PK sample.
10. Only drug screening and alcohol breath test.
11. Evaluate vital signs at baseline, 10 minutes after and 1hour post infusion/injection and in case of suspicion of hypersensitivity reaction including anaphylactic reaction.
12. AEs and concomitant therapies will be recorded throughout the trial, but will be specifically asked for at the time points indicated in the Flow Chart above.

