1.2.3 Nonclinical pharmacokinetics

Spesolimab has a very weak binding affinity to cynomolgus monkeys. Its pharmacokinetics (PK) characteristics in cynomolgus monkeys therefore addresses only the overall catabolic stability and FcRn recycling properties of the molecule, rather than full PK evaluation including possible specific target-mediated drug disposition. The PK of Spesolimab in cynomolgus monkeys were approximately dose linear following the IV administration of 0.3, 1.5, and 10 mg/kg of Spesolimab. The clearance, steady-state volume of distribution, and terminal half-life ($t_{1/2}$) for the three dose groups were similar ranging from 0.168-0.219 mL/h/kg, 65.2-83 mL/kg, and 284-349 h, respectively. The SC bioavailability was 62.6% [[n00243168](#)]. Anti-drug antibodies (ADA) were observed in both the 10 mg/kg IV and 1.5 mg/kg SC. dose groups, whereas the 0.3 and 1.5 mg/kg IV monkeys tested negative for ADA. In the two-week GLP toxicology study in CD-1 mice with Spesolimab, exposure increased proportionally from 10 to 50 mg/kg, and there was no apparent difference in Spesolimab serum exposure between male and female mice [[n00255537](#)].

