1.2.4 Prediction of human pharmacokinetics

PK data suggest TMDD kinetics for Spesolimab [[c09985235](#)]. The saturation of the non-linear elimination pathway is likely to occur after 0.3 mg/kg and Spesolimab exhibits linear kinetics from the next dose-level onwards up to 10 mg/kg. Based on the PK results in GPP patients, the elimination $t_{1/2}$ of Spesolimab was observed to be approximately three weeks in patients who are ADA-negative and approximately one week in patients who tested ADA-positive [[c17444370](#)]. Steady state was not attained after four weekly doses in the multiple dosing groups and the accumulation ratios were similar for the various dose groups. Preliminary PK data suggest the exposure of a 300 mg SC dose of Spesolimab is similar when administered as a single 2 mL injection or two separate 1 mL injections, which potentially provides flexibility to dose 300 mg with either 1 mL or 2 mL pre-filled syringes in future trials.

Pharmacodynamic (PD) effects in this first-in-human (FIH) single-rising-dose trial [[c03361085](#)] were assessed by indirect target engagement (ITE) of IL36R by Spesolimab using an ex vivo whole blood stimulation assay. Preliminary analyses indicate that >99% peripheral IL36R receptor occupancy is achieved with doses ≥ 1 mg/kg from 30 minutes post infusion to ten week.

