In the single-rising-dosing trial in Japanese healthy subjects 1368-0009, 32 healthy Japanese male subjects were enrolled in four dose groups each comparing eight subjects per group. The trial consisted of three dose groups receiving single rising IV infusion doses of Spesolimab (300 mg, 600 mg, and 1200 mg) and one dose group receiving single SC doses of Spesolimab (300 mg). In each dose group, 6 subjects received Spesolimab and two subjects' placebo. A total of three of 18 subjects (16.7%) on IV doses of Spesolimab (one subject per IV dose level) were reported with an AE compared with two of eight subjects (25%) on placebo. No subject was reported with an AE following subcutaneous administration of spesolimab. AEs by preferred term reported on placebo were vomiting, chest comfort, and allergic rhinitis, while AEs reported on Spesolimab were upper respiratory infection (300 mg IV), contusion (600 mg IV), gastroenteritis (1200 mg IV), and temporomandibular joint syndrome (1200 mg IV). None of the observed AEs were judged by the investigator as related to the trial medication. SAEs, deaths, AEs of special interest (AESI) or other significant AEs (according to project definition) were not observed and no subject discontinued the trial due to an AE. The overall AE frequency following administration of single doses of 300 to 1200 mg IV or 300 mg SC. Spesolimab was comparable with placebo.

In 1368-0001 and 1368-0002 trials, TMDD-related PK profile was observed. The exposure showed dose-proportional profile from 0.05 mg/kg to 20 mg/kg in single IV infusion group. In 1368-0009 trial, the exposure was also dose proportional within the evaluated dose range (300 mg to 1200 mg). No severe AE was observed in the each trials.

The relative bioavailability trial 1368-0029 explored PK as well as safety and tolerability of an SC formulation of Spesolimab in four treatment groups [periumbilical injection of 300 mg SC given at one (x 2 mL) or two (2 x 1 mL) injection sites, periumbilical injection of 600 mg SC (2 x 2 mL) and 300 mg SC (1 x 2mL) given to the thigh]. A total of 48 subjects entered the trial and completed the planned observation time according to the clinical trial protocol. To sum up, Spesolimab was safe and well tolerated by the healthy subjects and no safety signal was identified in trial 1368-0029.

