7.2 NULL AND ALTERNATIVE HYPOTHESES

It is not planned to test any statistical hypotheses in this trial.

Any confidence intervals computed are to be interpreted in the perspective of the exploratory character of the trial; i.e., confidence intervals are considered as interval estimates for effects.

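### Should the SAP prespecify an analysis of AUC0-∞ by anti-drug-antibody status alongside the dose-proportionality slope?

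*SAP*

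**What the plan says.** Dose proportionality after IV dosing is part of the primary objective. SAP 7.4.1 fits log AUC0-∞ and log Cmax on log dose over 450, 900 and 1200 mg in the PK parameter set, and reports the slope with a two-sided 90% interval. There is no ADA term, and the PK parameter set is not restricted by ADA status. The next section, "Sensitivity analysis, subgroup analysis, exploratory analysis of the primary endpoints", is entered as not applicable.

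ADA appears in the visible SAP as a safety variable with its own summary: "Descriptive data analysis of ADA will be performed by the department" is the statement in SAP 7, with output planned for CTR Section 15.8. Sampling is dense. Footnote 8 of the IV flow chart says "ADA samples will be taken at baseline, Day 15, Day 29, Day 43, Day 57, Day 71, Day 92", and it goes on to Days 120, 148 and 176. At the IV interim, PK and ADA data arrive together: "This interim lock includes the complete clinical data of the iv group, inclusive PK/ADA data".

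On interpretation, Protocol 7.2 plans no hypothesis test and says: "Any confidence intervals computed are to be interpreted in the perspective of the exploratory character of the trial".

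**The concern.** AUC0-∞ depends on clearance, and the protocol's own clinical data suggest that ADA changes elimination: Protocol 1.2.4 gives a half-life of "approximately three weeks in patients who are ADA-negative and approximately one week in patients who tested ADA-positive" in patients with generalised pustular psoriasis (GPP). If ADA-positive subjects fall unevenly across the three IV groups, the fitted slope moves away from 1 even though disposition is linear in dose. The same section describes target-mediated disposition, so a reader who sees a slope off 1 would ask about non-linearity, and the visible plan has no step that separates the two explanations. An ADA analysis added at reporting would be chosen after the slope is known. At stake is the explanation of a primary result, not a pass or fail decision.

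**Working it through.** **Inputs from the documents.** IV doses 450, 900 and 1200 mg; 10 evaluable subjects per group (Protocol 7.7); half-life 3 weeks (ADA-negative) and 1 week (ADA-positive), from GPP patients (Protocol 1.2.4).

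**Assumptions.** The documents give no ADA rate, onset time or dose gradient in healthy subjects, and no CV for AUC0-∞. Shares, onset times and CVs below are assumed.

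**Sample size.** The plan has no power calculation to reproduce. The totals agree: 5 × 10 = 50 evaluable, plus 10 replacements = 60. The IV regression uses 3 × 10 = 30.

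**Step 1: effect on one subject's AUC0-∞.** With k0 = ln 2/3 and k1 = ln 2 per week, and elimination switching from k0 to k1 at week T (one compartment), the ratio to the ADA-free AUC is 1 − exp(−k0·T)·(1 − k0/k1), where k0/k1 = 1/3.

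| Onset T (weeks) | AUC ratio | ln ratio |
|---|---|---|
| 2 | 0.580 | −0.545 |
| 4 | 0.735 | −0.307 |
| 6 | 0.833 | −0.182 |
| 12 | 0.958 | −0.043 |

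Week 2 corresponds to the first post-dose ADA sample (Day 15).

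**Step 2: shift in the slope.** Centred log doses are −0.558, 0.135 and 0.423, with sum of squares 0.508. For ADA-positive shares p in the three groups, shift = Σ(centred log dose × p) × ln ratio / 0.508. For 20/10/0% the sum is −0.558 × 0.2 + 0.135 × 0.1 = −0.098; for 40/20/0% it is −0.196.

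| Shares at 450/900/1200 mg | Week 2 | Week 4 | Week 6 | Week 12 |
|---|---|---|---|---|
| 20/10/0% | +0.105 | +0.059 | +0.035 | +0.008 |
| 40/20/0% | +0.210 | +0.119 | +0.070 | +0.016 |
| equal shares | 0 | 0 | 0 | 0 |

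Reversed gradients give the same values with a minus sign.

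**Step 3: precision of the planned slope.** SE = √ln(1 + CV²) / √(10 × 0.508), and the 90% half-width is 1.701 × SE (28 df).

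| Assumed CV | SE | 90% half-width |
|---|---|---|
| 20% | 0.088 | 0.149 |
| 25% | 0.109 | 0.186 |
| 30% | 0.130 | 0.221 |

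Every shift in Step 2 with onset at week 4 or later is at most 0.119, inside the half-width at all three CVs. At CV 25% only 40/20/0% with onset at week 2 (0.210) lies outside. On the r-fold scale with r = 1200/450, shifts of 0.059 and 0.119 are factors of 1.06 and 1.12.

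**Step 4: a longer baseline half-life.** Protocol 3.2 uses four weeks. Then k0/k1 = 1/4 and the ratio is 0.470 at week 2 and 0.625 at week 4. Three of 10 affected at 450 mg only would shift the slope by +0.249 (week 2) or +0.155 (week 4); three of 10 at 1200 mg only, by −0.189 or −0.117. At CV 25% the week-2 values pass 0.186 and the week-4 values do not.

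**Step 5: what an ADA-adjusted refit would deliver.** Add an ADA indicator to the power model and take its variance from σ²(X′X)⁻¹ with 27 df (t = 1.703) at CV 25%. With two ADA-positive IV subjects, the 90% half-width of the ADA coefficient is between 0.307 (one at 450 mg, one at 1200 mg) and 0.329 (both at 450 mg). The modelled effect is −0.307 at week 4 and −0.182 at week 6. The interval would therefore usually be compatible with both no ADA effect and a large one.

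**Step 6: whether IV Cmax separates the explanations.** It does not. IV Cmax falls near the end of a 90-minute infusion and depends little on clearance, so it would look proportional under either explanation.

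**The case for a change.** The best case for acting is that the protocol supplies the mechanism, that dose proportionality is a primary aim, and that a supportive display costs almost nothing. Among the IV groups in the monkey study, ADA appeared only at the top dose, so an uneven share is not purely hypothetical. With 10 subjects per group, chance alone can also produce imbalance: at a true share of 20% in every group, the chance shift has an SD of 0.097, 0.055 or 0.032 for onset at week 2, 4 or 6.

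Part of this stands. An early and strongly uneven ADA response could move the slope by more than its interval half-width, and a table of AUC0-∞ by dose group and ADA status would help a reader.

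The rest is weaker than it looks. Chance imbalance with equal true shares is extra between-subject scatter, which the residual variance and hence the interval already carry. In the same monkey study the PK results "were approximately dose linear following the IV administration of 0.3, 1.5, and 10 mg/kg". Protocol 1.2.5 reports proportional exposure from 300 to 1200 mg IV in healthy Japanese subjects, which spans all three doses here. Prespecification protects little where nothing is tested and the data are open-label throughout. An indicator model also conditions on a post-dose variable that may itself depend on dose.

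**Conclusion.** No change to the plan is needed. The power model without an ADA term estimates how exposure changes with dose in the subjects studied, whatever their ADA status, and that is what the objective asks for. Protocol 7.2 makes the interval an estimate only, so no decision can go wrong.

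The visible gap is one that analysts fill sensibly. All nine post-dose ADA visits are also PK visits, SAP 7 lists the individual values of all subjects, and SAP 7.4.1 plans graphical checks and a regression plot. If the slope departs from 1, the ADA-positive profiles among 30 IV subjects can be examined directly. Tabulating AUC0-∞ by ADA status, or marking those subjects on the plot, is an optional reporting choice.

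Nor is it established that the plan lacks such a display. SAP 7 refers inferential PK analyses to Section 7.6 and interim details to Section 9.1, neither of which is visible, and the content of the CTR 15.8 ADA summary is not spelled out.

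On size: with the three-week baseline and the assumed shares, the shift runs from 0 to 0.12 for onset at week 4 or later, against a half-width of 0.186 at CV 25%. It reaches 0.21 only for 40/20/0% with onset at week 2. These figures rest on a half-life contrast from GPP patients and on assumed ADA shares, onset times and CV.

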7.5 SECONDARY ENDPOINTS

7.5.1 Key secondary endpoint

This section is not applicable as no key secondary endpoint has been specified in the protocol.

7.5.2 Secondary endpoints

Refer to TSAP [Section 7.8.1](#) for a description of the analysis of adverse events.

7.7 EXTENT OF EXPOSURE

Descriptive statistics are planned for this section of the report based on the TS. The date and time of drug administration will be listed for each subject.

